7.7 Efficacy Analysis

7.7.1 Primary Efficacy Analyses:

The 2 primary efficacy endpoints of PFS and OS will be compared between CMB305 and placebo. Overall survival is defined as the time from randomization to the date of death.

Progression-free survival by investigator's assessment is defined as the time from randomization to the investigator-determined (using RECIST v1.1) date of disease progression or death. Radiographic images will be collected and assessed using RECIST v1.1 until the time the subject begins a new line of treatment.

For the purpose of PFS analysis, any one of the following events, whichever occurs first, will be used:

- Disease progression per RECIST v1.1 (See Appendix 1 [Table 7 \[Eisenhauer 2009\]](#))
- Symptomatic deterioration (global health deterioration) as described by RECIST v1.1
- For subjects with NED at time of randomization, any new malignant lesion that occurs after randomization per RECIST v1.1 (See Appendix 1 [Table 8](#))

Otherwise, subjects who do not have disease progression or have not died will be censored at the date when the last tumor imaging assessment determines a lack of progression. If a subject begins a new anti-cancer therapy or has radiotherapy, surgery, or other local regional therapy at a lesion site prior to documented progression, the subject will be censored at the last assessment where the subject was documented as progression free prior to the intervention. For subjects with NED at study entry, the appearance of a new malignant lesion as per RECIST v1.1 is defined as an event of progression for the purpose of PFS analysis. Subjects with 2 or more missing

response assessments (except for subjects with symptomatic deterioration) prior to a visit with documented progression (or death) will be censored at the last visit where the subject was documented to be progression free. PFS, by investigator's assessment, will be the primary PFS analysis. PFS by independent radiological review will be the supportive analysis.

The null hypothesis of no difference in OS/PFS between CMB305 and placebo, will be tested using a stratified log-rank test stratified by: disease status at screening (locally advanced unresectable versus metastatic), tumor response during screening (PR/SD versus CR/ NED), and by baseline presence of anti-NY-ESO-1 antibody (yes versus no)).

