**Table 3: Censoring Rules for PFS Analysis**

Situation	Date of Censoring	Outcome
No investigator-determined PD or death at the time of study discontinuation	Date of last adequate tumor assessment with no evidence of PD on or before study discontinuation	Censored
Investigator-determined PD or death after 2 or more consecutive missed tumor assessments	Date of last adequate tumor assessment with no evidence of PD that is before the first missed assessment	Censored
Investigator-determined PD or death after the start of subsequent intervention	Date of last adequate tumor assessment with no evidence of PD that is before the first subsequent intervention	Censored
No baseline and/or adequate post baseline tumor assessments or death at time of study discontinuation	Date of randomized	Censored

\* Adequate tumor assessment: tumor assessments with CR, PR, or SD as overall tumor response.

PFS by independent radiological review, if required, will be the supportive endpoints and follow similar definition and censorship as PFS by investigator's assessment, except that only PD from independent radiological review will be included as PD (symptomatic deterioration and clinical PD will not be included as PD).

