## **9 CHANGES FROM THE PROTOCOL SPECIFIED STATISTICAL ANALYSES**

If discrepancies exist between the text of the statistical analysis as planned in the protocol, and the final SAP, a protocol amendment will not be issued and the SAP will prevail.

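### SAP Table 3 censors PFS at a subsequent intervention only if PD or death follows, so event-free time after an intervention can count while events after it do not

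*SAP*

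**What the plan says.** Two rows of SAP Table 3 bear on a subject who has an intervention before PD.

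- **Row 3.** Situation: "Investigator-determined PD or death after the start of subsequent intervention". Censoring date: "Date of last adequate tumor assessment with no evidence of PD that is before the first subsequent intervention".
- **Row 1.** Situation: "No investigator-determined PD or death at the time of study discontinuation". Censoring date: "Date of last adequate tumor assessment with no evidence of PD on or before study discontinuation". An intervention does not limit this date.

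Row 2 (missed assessments before an event) and row 4 (no baseline or adequate post-baseline assessment) do not mention interventions.

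Protocol section 7.7.1, like the Synopsis, has no condition on later events. "If a subject begins a new anti-cancer therapy or has radiotherapy, surgery, or other local regional therapy at a lesion site prior to documented progression", then "the subject will be censored at the last assessment where the subject was documented as progression free prior to the intervention". For differences between the two documents, SAP section 9 says that "a protocol amendment will not be issued and the SAP will prevail".

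Four other places set the reach of the rule:

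- SAP section 5.1.2.1 counts anticancer therapy, cancer-related surgery and local regional therapy as subsequent interventions.
- Protocol section 7.7.1 ends image collection when a new line of treatment starts, whereas sections 3.1.4 and 6.3.1.3 continue imaging until PD.
- Protocol section 5.8.2 prohibits most such interventions before PD during the treatment period.
- SAP section 8.2.2.2 has two relevant PFS sensitivity analyses. One counts subsequent anti-cancer therapy as an event; the other treats its start as a competing event.

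**The concern.** The log-rank test and the Cox model need censoring that carries no information about the later event time, given arm and strata. Under Table 3 as written, the censoring date of a subject with an intervention is settled by what happens afterwards. If PD or death follows, the subject leaves the risk set before the intervention and the event is not counted. If nothing follows, the subject stays in the risk set up to the last scan. Time after an intervention thus enters the analysis only when it contains no event, which lowers the apparent hazard in whichever arm has more such time.

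PFS is one of two primary endpoints, and success on either defines study success (SAP sections 7.3 and 8.2.2.1). A censoring rule that can move the PFS hazard ratio in either direction should not rest on loose wording.

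**Working it through.** **1. The two rules on the 8-weekly scan schedule.** Take two subjects who have local therapy between the week 16 and week 24 scans, before PD, with scanning continued.

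| Later course | Protocol 7.7.1 | SAP Table 3 as written |
|---|---|---|
| PD at week 40 | censored at week 16 | row 3: censored at week 16 |
| No event, last scan week 48 | censored at week 16 | row 1: censored at week 48 |
| No event, imaging stopped at the intervention | censored at week 16 | row 1: censored at week 16 |

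The rules differ only in the second line. Both count the same events, so the 141-event trigger is the same under either; only the risk sets differ.

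**2. The plan's own figure.** Schoenfeld events for HR 0.55, 1-sided alpha 0.0125, 90% power, 1:1: 4 × (2.2414 + 1.2816)² / (ln 0.55)² = 4 × 12.41 / 0.3574 = 139, against 141 stated. Power at 141 events is 90.5%. The design figure is reproduced and is not in dispute.

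**3. Simulation with fixed shares.** From the documents: placebo median PFS 4 months, 124 per arm, the stated enrolment pattern, 8-weekly scans, analysis at the 141st event. Assumed, because the documents give nothing: exponential PFS, the share with an intervention before PD, scanning that continues afterwards, and a post-intervention hazard of 1.0, 0.5 or 0.25 times the earlier one. There were 1,500 trials per scenario, with an unstratified log-rank test. The Monte Carlo standard error of a 1.25% rejection rate is about 0.3 points.

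No true effect:

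| Share placebo / CMB305 | Mean HR, SAP as written | 1-sided rejection (nominal 1.25%) |
|---|---|---|
| 10% / 10% or 20% / 20% | about 1.00 | 1.0% to 1.5% |
| 10% / 20% | 0.965, 0.935, 0.916 | 1.9%, 3.9%, 5.2% |
| 10% / 30% | 0.917, 0.861, 0.811 | 4.5%, 9.6%, 19.1% |
| 20% / 10% | 1.040, 1.072, 1.097 | 0.9%, 0.0%, 0.3% |

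The triplets follow the hazard multipliers 1.0, 0.5 and 0.25. The protocol rule gave HR about 1.00 and rejection of 0.7% to 1.8% throughout. With equal shares, the SAP rule lengthened both medians by 0.1 to 0.5 months. In the 10% / 20% case, about 32 subjects had an intervention and 12 to 21 of them were event-free afterwards; those few subjects produce the shift.

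Design effect, HR 0.55: the protocol rule gave 88% to 90% power. The SAP rule gave:

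- 88% to 84% at 10% / 10%
- 86% to 72% at 20% / 20%
- 83% to 59% at 20% placebo / 10% CMB305
- 90% to 93% at 10% placebo / 20% CMB305

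**4. Constant monthly rates.** The placebo PFS hazard is ln 2 / 4 = 0.1733 per month. Under the null, the share with an intervention before PD is 0.02 / (0.02 + 0.1733) = 10% at 2% per month and 0.05 / (0.05 + 0.1733) = 22% at 5%, before allowing for scan timing and cutoff. With those, simulation gives about 9–10% and 20–28%. The null HR becomes about 0.94–0.98 if CMB305 has the higher rate and 1.03–1.07 if placebo has. Equal rates leave it at about 1.00.

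Equal monthly rates are not equal shares once there is a true effect. At HR 0.55 the CMB305 hazard is 0.55 × 0.1733 = 0.0953, so 5% per month gives 0.05 / (0.05 + 0.0953) = 34% there against 22% on placebo.

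**5. Scale.** With 141 events the standard error of the log HR is about 2/√141 = 0.168. A null HR of 0.94 is ln 0.94 = −0.062, or 0.37 standard errors. The 1-sided rejection rate is then roughly Φ(−2.2414 + 0.37) = 3.0%. For 0.98 it is Φ(−2.2414 + 0.12) = 1.7%.

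**The case against.** The strongest reply concerns reach, not the reading of the table.

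- **Imaging.** Row 1 censors at a scan, not at last contact. If imaging stops at a new line of treatment, as Protocol section 7.7.1 says, rows 1 and 3 give the same date and the effect is nil. This stands for new systemic lines. It does not cover surgery or local regional therapy that is not a new line, where sections 3.1.4 and 6.3.1.3 keep imaging going until PD.
- **Prohibition.** Section 5.8.2 bars most of these interventions before PD while on treatment. Some of its exceptions, such as symptomatic deterioration, are themselves PFS events. This stands and lowers the expected number. Subjects who stop study drug without PD remain exposed (Protocol section 6.5.2 keeps them in imaging follow-up).
- **Arm difference.** A shift in the null HR needs unequal intervention rates in a double-blind trial. This also stands: equal rates are the natural base case, and there the null HR is unbiased.
- **Sensitivity analyses.** Those in SAP section 8.2.2.2 could reveal a material dependence on subsequent therapy. They do not change the primary test.
- **Silence filled by the protocol.** One may argue that Table 3 simply omits this subject and the protocol rule applies. But row 1 does describe the subject, and the SAP has precedence over the protocol.

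**Conclusion.** The point holds as a defect in the governing text. Table 3 makes censoring on a primary endpoint depend on the later outcome, and it departs from the unconditional protocol rule.

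Its size cannot be fixed from the documents, which give no intervention rates. It is zero where imaging stops at the intervention. It can arise mainly for surgery or local regional therapy that is not a new line of treatment, with imaging continued to PD. The null HR ranges of 0.94–0.98 and 1.03–1.07 rest on assumed rates of 2% and 5% per month and on continued scanning. Equal rates leave the null HR at about 1.00, with some distortion of medians and a possible loss of power.

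A reader might infer three stronger things that the documents do not support:

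- **That the rule favours CMB305 or inflates the type I error.** The direction depends on which arm has more interventions before PD, and nothing in either document says which that is.
- **That every subject who starts new therapy is affected.** The stop to image collection at a new line, and the prohibition during treatment, argue against it.
- **That the sponsor meant to change the rule.** The sensitivity analyses use the start of therapy itself as the trigger, which suggests a drafting slip.

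**What to change.** Reword the situation in row 3 of SAP Table 3 to: *Start of subsequent intervention before investigator-determined PD or death (whether or not PD or death follows)*. Keep the present censoring date. Add that this row takes precedence over row 1.

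The cost is one table row and a short precedence note. The 141-event target and the sensitivity analyses stay as they are, and the SAP then agrees with Protocol section 7.7.1. If the programming already follows the protocol rule, nothing else changes.

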##### 5.1.1.1 Progression-free Survival (PFS)

PFS by investigator's review will be the primary endpoint. PFS by investigator's assessment is defined as the time from randomization to the investigator-determined (using RECIST v1.1) date of disease progression or death, whichever comes first:

[PFS = investigator-determined PD date or death date – randomization date + 1].

Investigator-determined PD event includes the followings:

- Disease progression per RECIST v1.1
- Symptomatic deterioration (global health deterioration) as described by RECIST v1.1
- For subjects with NED at time of randomization, any new malignant lesion that occurs after randomization per RECIST v1.1

PFS will be right-censored based on Table 3 for subjects who meet the following conditions:

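### SAP Table 3, row 4 has no 'no progression' condition: read literally, it censors at randomization a living subject whose first post-baseline scan shows PD, against the SAP's own PFS event definition

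*SAP*

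**What the plan says.** SAP 5.1.1.1 defines the endpoint as "PFS = investigator-determined PD date or death date – randomization date + 1". It then lists what counts as investigator-determined PD: "Disease progression per RECIST v1.1", symptomatic deterioration, and a new malignant lesion in a subject with NED at randomization. It continues: "PFS will be right-censored based on Table 3 for subjects who meet the following conditions".

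The rows and footnote of Table 3 that matter here are:

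- Row 1 covers "No investigator-determined PD or death at the time of study discontinuation". It names both PD and death.
- Rows 2 and 3 censor a PD or death that follows two or more consecutive missed assessments, or a subsequent intervention. Both say openly that they act on a PD.
- Row 4 covers "No baseline and/or adequate post baseline tumor assessments or death at time of study discontinuation", with censoring date "Date of randomized". It names death but not PD.
- The footnote reads "Adequate tumor assessment: tumor assessments with CR, PR, or SD as overall tumor response".

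Protocol 7.7.1 lists the PFS events first and only then turns to censoring: "subjects who do not have disease progression or have not died will be censored at the date when the last tumor imaging assessment" shows no progression. It has no counterpart to row 4. SAP Section 9 says the SAP prevails where the two documents differ.

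**The concern.** Take a subject who is alive and whose only post-baseline scan shows PD. PD is not CR, PR or SD, so by the footnote there is no adequate post-baseline assessment. There is no death. The conditions of row 4 are met, and the subject leaves the analysis at time zero. The event definition a few lines earlier makes the same scan a PFS event on the scan date. Both rules cannot be applied. The wording also catches symptomatic deterioration before any scan, and a new lesion at the first scan in a subject with NED.

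PFS is one of two primary endpoints. Censoring subjects at randomization because they progressed is informative. Under the design alternative it also removes more placebo than CMB305 events. What is at stake is the timing of the PFS analysis, the PFS estimates and, in one scenario, power.

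**Working it through.** **Inputs.** From SAP Section 4: 141 PFS events, HR 0.55, one-sided alpha 0.0125, 1:1 allocation, 124 per arm, placebo median 4 months, and 24-month accrual with 25% in year 1 and 75% in year 2. The implied CMB305 median is 4/0.55 = 7.27 months. Scans are every 8 weeks (protocol 3.1.3), and 56/30.4375 = 1.84 months. Exponential PFS is an assumption.

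**The plan's own figure.** Schoenfeld: events = 4(z₀.₉₈₇₅ + z₀.₉₀)²/(ln 0.55)² = 4(2.241 + 1.282)²/0.3574 = 139. Power at 141 events = Φ(½√141 × 0.598 − 2.241) = Φ(1.308) = 90.5%. The stated 141 events and 90% are reproduced.

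**Events by the first scan**, 1 − 2^(−1.84/median):

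- Placebo: 1 − 2^(−1.84/4) = 27.3%, or 33.9 of 124.
- CMB305: 1 − 2^(−1.84/7.27) = 16.1%, or 19.9 of 124.

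These include the few deaths before week 8, which row 4 does not touch.

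**Case A: row 4 applied literally to every first-scan event, and the trigger counts only events that survive it.** The log-rank test then compares subjects who are event-free past the first scan. Under exponential PFS the hazard ratio among them is still 0.55, so 141 remaining events still give about 90% power, and simulation gives 90%. The cut moves from about month 24.5 to about month 30 with detection at scans. With events at their exact times it moves from month 23.6 to 29.3. The Kaplan-Meier curve starts falling only after the first scan, so each median becomes 1.84 + m:

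- Placebo: 1.84 + 4 = 5.84 months, about 2 months too long.
- CMB305: 1.84 + 7.27 = 9.11 months, the same shift.

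**Case B: the trigger counts all true progressions, but the analysis censors every first-scan event.** In simulation (4,000 trials, 8-weekly detection, plan accrual) about 31 placebo and 18 CMB305 events are lost. About 91 of 141 remain, and log-rank power falls from 89.6% to 71.8%; other simulation runs gave 71% to 74%. The analytic version with exact event times loses 29.1 + 17.2 = 46.3 events. That leaves 94.7 events and Schoenfeld power of 74.8%.

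**Case B, sparing those who have died.** Row 4 does not reach a first-scan progressor who has died. Assume a median OS between 7.8 months (the figure protocol 1.1.2 cites after two prior lines) and 33.9 months (20/0.59, the design value for CMB305). Averaging 2^(−follow-up/median) over the accrual pattern at month 23.6 gives 47% to 82% still alive.

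| Share of about 49.6 first-scan events censored | Events left | Power |
|---|---|---|
| 47% | 141 − 0.47 × 49.6 ≈ 118 | 84% |
| 82% | 141 − 0.82 × 49.6 ≈ 100 | 77% |
| 100% (bound) | about 91 | 71–72% |

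**The case against.** The strongest reply is that no one would read the table this way. The event definition lists RECIST progression without qualification. Where Table 3 means to censor a PD, in rows 2 and 3, it says so. The protocol puts events first and censoring second. The definition of an adequate assessment looks as if it was written for the censoring-date column. All of this stands as evidence of intent. It does not remove the contradiction, because the SAP sends any subject who meets a listed condition to censoring and states no precedence for events. The protocol's order can help in reading the row, but under SAP Section 9 it does not override it.

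A second reply also has force. Row 4 applies at study discontinuation, and PD moves a subject into Long-term Follow-up, which is not study discontinuation. On that reading, many first-scan progressors would still be on study at the PFS cut and outside row 4. But row 1 uses the same phrase and must reach subjects still on study if they are to be censored at all. So the phrase makes the reach of row 4 uncertain and does not settle it.

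A reader might infer that literal use cuts 141 events to about 91 and power from 90% to about 71%. The documents do not support that as the expected effect. SAP 8.2.2.1 triggers the final PFS analysis at 141 PFS events, and a progression that row 4 censors would not be one. The loss needs one rule for the count and another for the analysis, and it needs every early progressor to be alive.

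**Conclusion.** The point holds as a drafting defect in a primary-endpoint rule. As worded, row 4 gives the wrong result for a living subject whose first evidence of disease status after randomization is progression. It is not evidence that the sponsor plans to discard early progressions.

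Under the stated assumptions, the consequence of consistent literal use is a PFS cut about 6 months later and Kaplan-Meier estimates biased upward, by about 2 months for the placebo median. Power stays near 90%. Both shifts are at their largest here, because the calculation censors every first-scan event. Power is at risk only if the event count and the analysis follow different rules: about 84% to 77% with 47% to 82% of early progressors alive, and no lower than about 71%. The stability of the hazard ratio in Case A rests on a constant hazard ratio over time. The working does not cover a delayed treatment effect.

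**What to change.** Reword the row 4 situation to: *No investigator-determined PD and no death, and no baseline or no adequate post-baseline tumor assessment.* Add one sentence under Table 3: *Investigator-determined PD, as defined in Section 5.1.1.1, is a PFS event unless row 2 or row 3 applies.* Redefining an adequate assessment to include PD is optional once row 4 carries the no-PD condition.

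The cost is two lines of SAP text, to be settled before unblinding and database lock. Sample size, event target and trial conduct do not change.

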### 5.1.1.2 Overall Survival (OS)

OS is defined as the time from randomization to the date of death from any cause:

[OS = death date – randomization date + 1].

Any subject without a date of death in the database at the time the survival analyses are performed will be censored at the date of last known alive. The date of death is recorded on the death report form page. The last known alive date is defined as the last date the subject was known to be alive at the study. The last known alive date will be the latest date among the following:

- Last assessment date among, e.g., vital signs assessment, performance status assessment, tumor imaging, and assessment date in third-party data such as central laboratory, ECG etc.
- Last adverse events date
- Last known alive date collected on the 'Long-term Follow-up' page of eCRF
- Date of last contact in 'End of Study' page of the eCRF

- Last date among last study treatment, and last concomitant medications, subsequent interventions administered after study treatment discontinuation.

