- ^p Peripheral blood will be collected at the following times after administration of the first dose of study drug on Day 1: no sooner than Day 92 (3 months) but up to 4 months; 6 months up to 9 months; and 1 year up to 15 months; and then yearly at no sooner than every 12 months but not more than 15 months up to the time of study closure. If all post-treatment assays are negative during the first year, then the yearly samples should be archived. Samples will be used for an assay to test for persistence of LV305.
- ^q The Day 92 biopsy may be obtained within ± 2 weeks of Day 92, Day 365, and at time of progression event will be encouraged at the same selected US sites per footnote “g”.
- ^r Survival status will be obtained by any means, which includes, but is not limited to, public records where allowed per local authority, telephone contact, during an in-clinic visit, chart review, or via communicating with an individual (e.g., family, friend, referring health care provider) who is knowledgeable of the subject’s survival status. More frequent survival status updates may be obtained at the request of the sponsor.

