## 7.2 Handling of Dropouts or Missing Data

In order to achieve the goal of a well-conducted clinical study according to Good Clinical Practice, every effort will be made to collect all data. However, despite best efforts, it may be inevitable that some data may be missing or incomplete.

In the subject data listing all available data, including partial data, will be presented as they are recorded on the case report forms (CRFs).

Time to event or duration of event endpoints will be calculated based on the study day of the event date (or censoring date) rather than visit number or visit label. Missing efficacy or safety data will not be imputed unless otherwise specified.

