### 7.2.1 Partial Dates for Adverse Events

For adverse events (AEs) with partially missing start dates, it's necessary to impute an AE start date to define TEAE. For the partial date of AE start date (missing day and/or month and/or year), the following imputation rules will be applied:

- If year of the AE start date is missing, no date imputation will be made and the AE will not be considered treatment-emergent unless the investigator has deemed it to be treatment-related.
- If both day and month of the AE start date are missing but year is known, the day and month will be imputed with the day and month of the first study dose date if the year is equal to the year of first dose. Otherwise, the month and day is imputed as the first day of the year (01 Jan).
- If only day is missing, and if the year and month are equal to the first dose date, the day will be imputed as day of the first dose date. Otherwise, the day will be imputed as "01."

Partial AE end dates will be imputed for non-ongoing AEs as follows:

- If year of the AE end date is missing, no date imputation will be made.
- If both day and month of the AE end date are missing but year is known, the date of the last dose of study drug will be used as the end date of the AE. Otherwise, December 31 will be used as the end of the AE.
- If only day is missing, the date of last dose of study drug will be used as the end date of the AE. Otherwise, the last day of the month will be used as the end of the AE.

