### 7.2.2 Partial Dates for Concomitant Medication

For concomitant medications (CM) with incomplete dates, imputation will be used to convert to a complete date. Imputed dates will be used to determine Study Day.

Partial medication start dates will be imputed as follows:

- If year of the CM start date is missing, no date imputation will be made.
- If both day and month of the CM start date are missing but year is known, the day and month will be imputed with the day and month of the first study dose date if the year is equal to the year of first dose. Otherwise, the month and day is imputed as the first day of the year (01 Jan).
- If only day is missing, and if the year and month are equal to the first dose date, the day will be imputed as day of the first dose date. Otherwise, the day will be imputed as “01.”

Partial medication end dates will be imputed for non-ongoing medications as follows:

- If year of the CM end date is missing, no date imputation will be made.
- If both day and month of the CM end date are missing but year is known, the date of the last dose of study drug will be used as the end date of the medication. Otherwise, December 31 will be used as the end of the medication.
- If only day is missing, the date of last dose of study drug will be used as the end date of the medication. Otherwise, the last day of the month will be used as the end of the medication.

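### In the primary OS analysis the SAP censors a known death that has no date, and it has no rule for a death that is only partly dated

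*SAP*

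**What the plan says.** SAP 5.1.1.2 defines the endpoint as "OS = death date – randomization date + 1", so a complete death date is needed to compute it. The censoring rule is "Any subject without a date of death in the database at the time the survival analyses are performed will be censored"; the censoring time is the latest evidence that the subject was living. On where the death date comes from, the section says "The date of death is recorded on the death report form page".

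SAP 7.2 (numbering in the body of the document) adds: "Missing efficacy or safety data will not be imputed unless otherwise specified". The only date imputation then specified is in 7.2.1 for adverse events (for example, "Partial AE end dates will be imputed for non-ongoing AEs as follows") and in 7.2.2 for concomitant medications.

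The OS definition in Protocol 7.7.1 has no rule for an incomplete death date. None of the sensitivity analyses in SAP 8.2.2.2 covers one: the OS competing-event analysis deals with definite loss to follow-up and withdrawal of consent.

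Protocol Table 2, footnote r, lets survival status come from any source, including "public records where allowed per local authority, telephone contact", chart review, and family or friends. Long-term follow-up runs for up to 5 years, with contacts every 3 months.

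**The concern.** The censoring rule asks whether a date is in the database, not whether the subject is known to have died. Applied as written, it turns a known primary event into a censored observation. Survival status gathered from relatives or public records can plausibly arrive as a month, a year, or simply the fact of death.

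Three things are at stake: events lost from the OS log-rank test, uncertainty over whether such deaths count toward the 120-death futility look and the 179-death final analysis, and a choice on a primary endpoint that might otherwise be made after unblinding.

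There is a related weakness in the censoring date. Last known alive is the latest of several dates, including the last adverse event and last concomitant medication dates. SAP 7.2.1 and 7.2.2 can complete those end dates to month end or 31 December, and 5.1.1.2 does not say whether completed dates are excluded. If they are used, a dead subject could be censored after the true date of death.

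**Working it through.** **Inputs** (SAP 4 and Protocol 7.1): 179 deaths, HR 0.59, one-sided alpha 0.0125, 90% power, 1:1 allocation, placebo median 20 months, 248 subjects, 24 months of enrolment (25% then 75%) and 42 further months. The share of deaths with an incomplete date is not given and is assumed.

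**1. The plan's own figure.** Schoenfeld: d = 4(z₀.₉₈₇₅ + z₀.₉₀)² / (ln 0.59)² = 4(2.2414 + 1.2816)² / 0.5276² ≈ 178.3, rounded up to 179. This matches the plan.

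**2. Power with fewer analysable deaths.** Power = Φ(√d/2 × |ln 0.59| − 2.2414). This applies if the trigger counts all 179 known deaths but the undated ones are then censored.

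| Share affected (assumed) | Deaths lost | Deaths analysed | Power |
|---|---|---|---|
| 0% | 0 | 179 | 90.1% |
| 1% | 2 | 177 | 89.8% |
| 2% | 4 | 175 | 89.4% |
| 5% | 9 | 170 | 88.5% |
| 10% | 18 | 161 | 86.6% |

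**3. If the trigger counts only dated deaths.** The event-based power loss disappears and follow-up lengthens instead: 179/0.98 ≈ 183 known deaths are needed at 2%, and 179/0.95 ≈ 189 at 5%. The plan's assumptions, with exponential survival and no dropout, give about 182 deaths at month 66.

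**4. Effect on the hazard ratio, by simulation.** 4,000 runs per scenario; exponential survival; cutoff at the 179th known death; undated deaths censored at the last 3-monthly contact; unstratified log-rank test; no futility stop.

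| Undated, placebo / CMB305 | Estimated HR (true 0.59) | Power | Estimated HR (true 1.0) | One-sided rejection |
|---|---|---|---|---|
| 0% / 0% | 0.584 | 90.1% | 1.001 | 0.0135 |
| 2% / 2% | 0.583 | 89.1% | 0.998 | 0.0140 |
| 5% / 5% | 0.586 | 88.0% | 1.002 | 0.0127 |
| 10% / 10% | 0.585 | 86.0% | 1.000 | 0.0122 |
| 0% / 5% | 0.557 | 93.6% | 0.953 | 0.0280 |
| 5% / 0% | 0.613 | 81.9% | 1.049 | 0.0050 |

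The Monte Carlo standard error of a rejection rate near 0.0135 is √(0.0135 × 0.9865/4000) ≈ 0.002. The equal-share rows therefore agree with the nominal 0.0125, and the 0.0280 does not.

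**The case against.** The strongest reply is that the gap will rarely matter. There is a dedicated death form, survival contact every 3 months, source verification and queries (Protocol 8.11 and 8.13), death and autopsy reports among the possible source documents (8.16), and a stated intention in SAP 7.2 to collect all data. The trial is double-blind with the same follow-up in both arms, so a marked imbalance in undated deaths is unlikely. With equal shares the hazard ratio does not move. All of this stands, and it limits the size of the problem. It does not supply the missing rule.

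A reader might infer more than the documents support:

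- **That the SAP says partly dated deaths are censored.** It does not say that a month or year on the death form counts as no date. That OS cannot be computed and nothing completes the date is an inference, though the text offers no other working rule.
- **That the lost deaths are concentrated in subjects who left the sites, so the loss is known to be non-random.** Nothing in either document shows this.
- **That a partly dated next therapy becomes a Day 1 TTNT event and censors PFS at baseline.** SAP 7.2.2 covers concomitant medications, and 5.1.1.2 lists subsequent interventions separately. Even if 7.2.2 were borrowed, its wording is conditional: "the day and month will be imputed with the day and month of the first study dose date if the year is equal". The comparison is with the year in which dosing began; a start in any other year goes to 1 January. For TTNT the documents support only that the SAP is silent on partial start dates of subsequent therapy.

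**Conclusion.** The gap is real. A known death with no date is censored by the express words of SAP 5.1.1.2, and a known death with a partial date has no rule that keeps it as an event. This should be fixed before database lock, but it does not undermine the design.

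The cost in power is about 0.7 to 1.6 percentage points (90.1% to 89.4% or 88.5%). That rests on three assumptions: 2% to 5% of deaths are affected, the shares are equal by arm, and the trigger counts all known deaths. If only dated deaths are counted, the cost is longer follow-up.

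It would be too strong to conclude that the primary hazard ratio is biased. That needs unequal shares. The 5% versus 0% split shows what an imbalance could do (rejection of about 0.028 under the null in one direction, power of about 82% in the other), but the split is hypothetical and nothing in the documents predicts it.

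**What to change.** Add to SAP 5.1.1.2 and 7.2:

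- A subject known to have died is an OS event, and a PFS event where the PFS censoring rules allow.
- Only the day missing: use the later of the 15th of that month and the day after last known alive.
- Year known, month missing: use the later of a fixed date in the recorded year (for example 1 July) and the day after last known alive, so that the recorded year is not discarded.
- Year unknown: use the day after last known alive.
- In every case, no later than the date the death was reported.
- Exclude imputed adverse event and medication end dates from the last-known-alive date.
- Count the 120 and 179 deaths on the same basis as the analysis.
- Add a sensitivity analysis that varies the imputed death dates.

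Separately, state how a partial start date of subsequent therapy is handled for TTNT.

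The cost is a short SAP revision and programming. No new assessments are needed; the one item to confirm is that the date on which each death was reported is captured.
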